A non-contrast cervical spine CT scan at will be obtained for research purposes at UVMMC at the 12 (+/-1) week time point. Final fracture characteristics (angulation, displacement) will be documented based on the 12-week CT scan. Amount of fracture healing will be assessed on CT by a radiologist by the following method¹⁰: 1 mm coronal and sagittal sections across the fracture will be individually analyzed. The radiologist will reconstruct the CT scan to true orthogonal coronal and sagittal images. Each slice will be analyzed for the width of bridging bone as a percentage of the width of the fracture line. The sum total of the widths of bridging bone, divided by the sum total of the fracture widths will be expressed as a percentage of total healing for that patient. This absolute % of bridging bone will be the primary outcome¹⁰. Fracture characteristics (obliquity, angulation, displacement, comminution) on the injury CT scan will be documented for later post-hoc analysis. Additionally, we will also compare our study group results to the union rates documented in the existing literature.

Control subjects:

Our historical control group will be comprised of patients with type II odontoid fractures (defined above) who were previously treated in our spine fracture clinic. Patients will have been injured within the past ten years, and have completed 12 +/-1 weeks of hard collar immobilization. Potentially eligible historical controls will be identified by database query and chart/radiographs review of patients from the fracture clinic. A request will be made of the UVMMC Data Management Office to identify potential control subjects. Identified potential control patients will be approached as outlined under 'Consent Process', below.

If patients are interested in active study participation by coming in for a study visit (research imaging: *Control cohort A: Active control participants*), written informed consent will be obtained in person at UVMMC by designated research personnel. Consented active control subjects will then complete a CT scan of the cervical spine for comparison to those from our study group. If flexion-extension cervical XR were not obtained 11 or more weeks after initiation of hard collar treatment as part of their routine care, flexion-extension cervical XR will be obtained for the study. Additionally, these control subjects will complete VAS Neck and NDI physical function questionnaires.

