For these control participants, the study team will collect information that is available in the electronic medical record to support analyses of available outcomes. This information includes demographic information, fracture characteristics and applicable radiographs obtained during their routine care for neck fracture.

Describe required screening procedures performed before enrollment and while on study.

Screening procedures for treatment subjects before enrollment:

At the time of spine surgical consultation, CT scans obtained for routine care will be evaluated and those patients whose fracture types meet the inclusion criteria will be approached to consider participation in the study. After consent is obtained, but prior to enrollment, patients will be screened for eligibility based on their medical history, as well as laboratory values. Laboratory values obtained for eligibility screening will include a Comprehensive Metabolic Panel, PTH and Phos. Based on medical history, Ca, PTH, and Phos levels an endocrinologist on the study team will confirm eligibility for the study prior to enrollment.

Screening procedures for treatment subjects while on study:

Cervical spine x-rays will be obtained at each clinic visit as per our routine non-operative management. These will be reviewed as outlined in Withdrawal Procedures, below.

For research involving survey, questionnaires, etc.: Describe the setting and the mode of administering the instrument and the provisions for maintaining privacy and confidentiality. Include the duration, intervals of administration, and overall length of participation.

Not applicable

Two questionnaires (VAS Neck and Neck Disability Index (NDI) physical function questionnaires) will be administered 3 times for each treatment subject (at each clinic visit: 4 weeks, 8 weeks, and 12 weeks), and once for each control subject. Together the two questionnaires can be completed in under 10 minutes.

For treatment subjects, the questionnaires are administered as part of routine care at these time points, as they are for other patients with dens fractures. The two questionnaires are integrated into our standard practice for all spine patients at clinic. The questionnaires are administered by medical staff in clinic prior to evaluation by the physician. They are completed privately by the patient and inserted into the patient's electronic health record after the visit.

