Statistical Considerations: Delineate the precise outcomes to be measured and analyzed. Describe how these results will be measured and statistically analyzed. Delineate methods used to estimate the required number of subjects. Describe power calculations if the study involves comparisons. Perform this analysis on each of the primary and secondary objectives, if possible.

Primary outcome will be % bridging bone on CT scan at 12 weeks as described previously based on 1 mm sagittal and coronal cuts. The study radiologist evaluating the primary outcome will be blinded to patient group (treatment vs. historical control). Secondary outcomes will include VAS Neck and NDI scores, and motion on flexion/extension radiographs.

Assuming 60% nonunion rate in our historical control group and 20% in our study group, with alpha = 0.05 and 80% power, we would need to enroll 44 patients in a randomized trial (22 control, 22 study patients) to show a statistical difference. This study is intended as an initial pilot study to suggest efficacy, and further inform a future randomized controlled trial. We see 15-20 new type II dens fractures treated non-operatively per year in our fracture clinic, and estimate the initial pilot of 10 treatment patients + 12 control subjects can be completed within 2 years.

Data analysis will be based on multi-variate regression using ANOVA, with $p < 0.05$ recognized as a significant difference. Plan is for as treated analysis; if there are patients who receive only partial course of study drug for any reason, they will be evaluated descriptively as a separate group. Additionally, we will also compare our study group results to the union rates documented in the existing literature.

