No. However, the proposal involves use as an experimental treatment of a fracture that is most common in elderly patients with osteoporosis, and the study drug is approved for the treatment of individuals with osteoporosis who are at high risk for these fractures.

SUBJECT CHARACTERISTICS, IDENTIFICATION AND RECRUITMENT

Subject Selection: Provide rationale for subject selection in terms of the scientific objectives and proposed study design.

The study population includes patients greater than or equal to the age of 50. This is the population that sustains dens fractures most frequently.

Vulnerable Populations: Explain the rationale for involvement of subjects (e.g., cognitively impaired, Non-English speaking, prisoners, students). Discuss what procedures or practices will be used in the protocol to minimize their susceptibility to undue influences and unnecessary risk (physical, psychological, etc.).

Not applicable

Inclusion/Exclusion Criteria: Eligibility and ineligibility criteria should be specific. Describe how eligibility will be determined and by whom. Changes to the eligibility criteria at a later phase of the research have the potential to invalidate the research.

Treatment Subjects

Inclusion Criteria (all must be yes)

1. Age 50 years or older at time of consent
2. Anderson and D'Alonzo type II dens fracture identified on cervical spine CT, with or without a C1 ring injury. Type II dens fractures are defined as involving the area of the dens between the inferior aspect of the anterior C1 ring and not extending into the superior articular facets of C2.
3. Fracture is deemed amenable to non-operative treatment by treating fellowship trained spine surgeon
4. Fracture occurred within the 3 weeks before consent
5. Report of ≥ 12 months of amenorrhea within the last year if the patient is female

Exclusion Criteria (all must be no)

6. Personal history of radiation therapy to the skeleton
7. Personal history of osteosarcoma
8. Personal history of Paget's disease
9. Personal history of bone metastases or skeletal malignancy
10. Hereditary disorders predisposing to osteosarcoma
11. Prior teriparatide or abaloperatide use
12. Use of denosumab within the past year
13. Psychological impairment that precludes following hard collar immobilization recommendations
14. Ineligible based on history of active or recurrent kidney stones, CMP, PTH, Phos results to be determined on a case-by-case basis by an endocrinologist on the study team

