Historical Comparison Subjects

Inclusion Criteria (all must be yes)

1. Age 50 years or older at time of fracture
2. Anderson and D'Alonzo type II dens fracture identified on cervical spine CT, with or without a C1 ring injury. Type II dens fractures are defined as involving the area of the dens between the inferior aspect of the anterior C1 ring and not extending into the superior articular facets of C2.
3. Fracture injury occurred within 10 years before consent
4. The patient completed 12 (+/- 1) weeks of hard collar immobilization

Exclusion Criteria (all must be no)

5. Any history of prior teriparatide or abaloperatide use
6. Use of denosumab in the past year

Inclusion of Minorities and Women: Describe efforts to include minorities and women. If either minorities or women are excluded, include a justification for the exclusion.

Women will be included in the study whenever the eligibility criteria are met. Every effort will be made to recruit minorities. Recruitment efforts will not differ by sex or by ethnicity.

Inclusion of Children: Describe efforts to include children. Inclusion is required unless a clear and compelling rationale shows that inclusion is inappropriate with respect to the health of the subjects or that inclusion is inappropriate for the purpose of the study. If children are included, the description of the plan should include a rationale for selecting or excluding a specific age range of children. When included, the plan must also describe the expertise of the investigative team in working with children, the appropriateness of the available facilities to accommodate children, and the inclusion of a sufficient number of children to contribute to a meaningful analysis relative to the purpose of the study. Provide target accrual for this population. Identify whether children are wards of the state. **If children are excluded** then provide appropriate justification.

The fracture of interest occurs very rarely in minor subjects, and the safety and effectiveness of the study drug has not been established in pediatric patients. Children will not be included in this study.

For protocols including the use of an investigational drug, indicate whether women of childbearing potential have been included and, if not, include appropriate justification.

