In all cases, subjects will be given as much time as they need to discuss the study with others and make their decision. However, treatment patients and comparison subjects will need to be enrolled within 3 weeks of fracture injury and 10 years of fracture injury, respectively, to be eligible for study participation (see Inclusion and Exclusion Criteria, above).

iii. Is the principal investigator present for the initial and subsequent informed consent discussions with the subject?

Either the PI or other designated key study personnel will be present for the initial and subsequent consent discussions with the subject.

iv. What other method of documentation is used to record the informed consent process, in addition to the executed consent form? See an [example of documentation](#) of the informed consent **process** under consent templates on our forms page.

Written informed consent processes will be documented using an Informed Consent Process Documentation form. This form is based on the standard IRB template and will be filed together with the informed consent form in the study folder for each consented subject.

Verbal consent processes will be documented using an Informed Consent Process Documentation form. This form will be maintained together with a record of the verbal consent script used for that subject.

Information Withheld From Subjects: Will any information about the research purpose and design be withheld from potential or participating subjects? If so, explain and justify the non-disclosure and describe plans for post-study debriefing.

Not applicable

Research Data Management Plan: The Research Data Management and Security Plan form must be completed. The form, along with guidance, can be found in our [forms library](#) and must be submitted with your initial application.

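### The control criteria let a patient screened out of the drug group on history or labs enter later as a historical control

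*Combined protocol and SAP*

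**What the plan says.** The protocol states the control window three times, and each time it rolls forward.

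- Inclusion/Exclusion Criteria, Historical Comparison Subjects: "Fracture injury occurred within 10 years before consent".
- Study Design, Control subjects: "Patients will have been injured within the past ten years". The same paragraph describes controls as patients "who were previously treated in our spine fracture clinic".
- Consent Process: "treatment patients and comparison subjects will need to be enrolled within 3 weeks of fracture injury and 10 years of fracture injury, respectively".

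None of these sets a latest injury date relative to the opening of the trial. The remaining control criteria are age, fracture type, and "The patient completed 12 (+/- 1) weeks of hard collar immobilization", plus two exclusions (earlier teriparatide or abaloparatide, and denosumab in the past year).

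The drug group is filtered further. Under the screening procedures for treatment subjects, "After consent is obtained, but prior to enrollment, patients will be screened for eligibility based on their medical history, as well as laboratory values". Treatment exclusions 6-10 remove patients with skeletal radiation, osteosarcoma, Paget's disease, bone malignancy or a hereditary osteosarcoma risk. Exclusion 14 reads "Ineligible based on history of active or recurrent kidney stones, CMP, PTH, Phos results", decided case by case by the study endocrinologist. The Therapeutic Alternatives section gives collar treatment without the drug as the alternative to taking part, which is what the controls received.

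**The concern.** The same team can judge a patient unsuitable for one group and later count that patient in the other, without breaking a written rule. The drug group would then consist of patients who passed the screen, while the control group could include some who failed it. The named laboratory reasons for exclusion are elevated PTH and hypercalcemia, and several history exclusions are bone diseases. If such patients heal less well, the contrast moves toward the drug for a reason unrelated to treatment.

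Nothing in the plan would reveal this. The radiologist is blinded to group, but blinding does not affect who enters a group. The analysis section names no covariates, Table 2 collects no labs from active controls, and screening status is not recorded as a variable. A reader would take controls labelled historical to predate the trial.

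**Working it through.** **1. The plan's own figure.** Statistical Considerations assumes 60% versus 20% non-union, alpha 0.05 and 80% power, and gives 22 per group. With a two-sided test and the arcsine formula, h = 2·asin(√0.6) − 2·asin(√0.2) = 0.845 and n = 2·((1.96 + 0.84)/h)² = 21.99, so 22 per group. The pooled normal formula gives 23. The figure reproduces. It describes a randomized trial, whereas the pilot has 10 treated and 12 controls; the present point does not depend on it.

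**2. Can a screen failure meet the control criteria?** Take a patient who consents to the drug group, is found ineligible on labs or on exclusions 6-10, and is managed in a collar.

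| Control criterion | Met? |
|---|---|
| Age 50 or older at fracture | Yes; the drug group has the same limit, at consent up to 3 weeks later |
| Type II dens fracture on CT | Yes, same definition |
| Injury within 10 years before consent as a control | Yes |
| 12 (+/-1) weeks of collar completed | Yes, if completed |
| No earlier PTH analog; no recent denosumab | Yes, unless these were the reason for failure |

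The route is open. Patients excluded for psychological impairment would be partly stopped by the completed-collar requirement.

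**3. Size of the pool.** Input from Statistical Considerations: "We see 15-20 new type II dens fractures treated non-operatively per year in our fracture clinic". A constant rate over ten years is assumed.

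- Ten years: 15 × 10 = 150 to 20 × 10 = 200. Minus 10 treated: N = 140 to 190.
- Two trial years: 30 to 40 cases. Minus 10 treated: 20 to 30 not enrolled, for any reason.

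**4. Expected screen failures among 12 controls.** The number of failures, s, is not given; 2, 5 and 10 are assumed. For a random draw, expected = 12·s/N, and P(at least one) = 1 − C(N−s, 12)/C(N, 12).

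| s | Expected (N = 190 to 140) | P(at least one) |
|---|---|---|
| 2 | 0.13 to 0.17 | 12% to 16% |
| 5 | 0.32 to 0.43 | 28% to 37% |
| 10 | 0.63 to 0.86 | 49% to 60% |

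If only half of the pool were usable but every screen failure remained in it, the expected counts would double, to between 0.25 and 1.71.

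**5. Shift per patient.** One control is 1/12 = 8.3% of the group. With non-union q in screen failures against the planned 60%, each shifts the control rate by (q − 0.60)/12:

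- q = 0.70: 0.8 points
- q = 0.80: 1.7 points
- q = 0.90: 2.5 points

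**6. Combined, under random selection.** Lowest: 0.126 × 0.83 = 0.1 points. Highest: 0.857 × 2.5 = 2.1 points. The planned difference is 40 points. Its standard error at 12 versus 10 is √(0.24/12 + 0.16/10) = 0.19, or 19 points.

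**The case against.** A reader might infer that the missing cut-off loads the control group with patients judged unfit for the drug, for example 3 or 6 of 12, adding 5 or 10 points of false effect at 80% non-union. The documents do not support that. They permit entry but report no screen failures. The 20 to 30 untreated patients in the trial years also include decliners, late presenters and patients never approached.

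Nor is it established that recent patients will dominate. Controls are found by database query, those with an existing post-collar CT need only verbal consent, and deceased patients enter by chart review; none of these routes favors the trial years. On the other side, a research CT needs a living patient willing to return, and approach in person is allowed, which favors recent patients. Some over-representation is possible, but its size is unknown.

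The direction of bias is also an inference. The risk sections tie the calcium and kidney-stone screen to drug safety, and no passage says these patients heal worse. Recent controls may even help, because active controls can otherwise be scanned years after injury while treated patients are scanned at 12 weeks.

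Finally, a date cut-off would not remove the wider cause: exclusions 6-10 and 14 apply to no control of any date. That objection stands and shapes the fix. The others limit the size of the point; none closes the route.

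**Conclusion.** The point holds as a gap in the eligibility rules. The words historical and previously treated suggest earlier patients but are tied to no date, so a patient who fails this trial's screen can later be a control under the criteria as written.

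The likely effect is small: fewer than one such patient among 12 under random selection, and a shift in the control non-union rate well inside the pilot's sampling error. This rests on three assumptions: 2 to 10 screen failures, a random draw from a constant ten-year case flow, and 70-90% non-union in screen failures. The shift is expressed on non-union because the plan gives planning rates only on that scale; the effect on percent bridging bone cannot be computed from the documents. The pilot is nevertheless meant to suggest efficacy and inform a randomized trial, and the gap costs little to close. It is a cheap improvement that should be made before controls are selected, and it is not evidence that the comparison is already biased.

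**What to change.** - Add a control exclusion: anyone screened for the treatment group and found ineligible on medical history or screening labs. Consent precedes screening, so these patients can be identified from the trial's own consent files.
- Apply treatment exclusions 6-10 to all controls, whatever the injury date. Sources of Materials already lists office notes and lab results for both control cohorts.
- Keep otherwise eligible patients who declined the drug, flag them as concurrent controls, and show the primary contrast with and without them. Someone who declined before consent will not have had the screening labs, so the report should say so. The protocol describes no screening log, so a short list of patients approached would have to be kept.

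The cost is two lines of eligibility text, one flag and one sensitivity comparison. A few controls are lost from a pool of roughly 140 to 190. The stated sample sizes and patient care do not change. A laboratory mismatch remains for pre-trial controls without recorded labs and should be reported as a limitation.

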Identified potential control subjects who (a) previously had a cervical CT after completion of hard collar treatment under routine care or (b) were offered participation in Control Cohort A but are not interested in active study participation (i.e. do not consent to come in for study visit) will be invited to verbally consent to allow the study team to collect existing information that is available from their treatment for dens fracture in the electronic medical record, as outlined in 'Procedures for subjects in *control cohort B*', below.

For potential control subjects who are deceased at time of identification, the study team will collect existing information that is available from their treatment for dens fracture in the electronic medical record, as outlined in 'Procedures for subjects in *control cohort B*', below.

All research-driven CT scans will be obtained at UVMMC with the proper imaging protocols and resolution.

9. Grauer, J. N., Shafi, B., Hilibrand, A. S., Harrop, J. S., Kwon, B. K., Beiner, J. M., ... & Vaccaro, A. R. (2005). Proposal of a modified, treatment-oriented classification of odontoid fractures. *The Spine Journal*, 5(2), 123-129.
10. Jones, C. P., Coughlin, M. J., & Shurnas, P. S. (2006). Prospective CT scan evaluation of hindfoot nonunions treated with revision surgery and low-intensity ultrasound stimulation. *Foot & ankle international*, 27(4), 229-235.

Procedures: Describe all procedures (sequentially) to which human participants will be subjected. Identify all procedures that are considered experimental and/or procedures performed exclusively for research purposes. Describe the types, frequency and duration of tests, study visits, interviews, questionnaires, etc.

Note: A clinical research protocol may involve interventions that are strictly experimental or it may involve some aspect of research (e.g., randomization among standard treatments for collection and analysis of routine clinical data for research purposes). It is important for this section to distinguish between interventions that are experimental and/or carried out for research purposes versus those procedures that are considered standard therapy. In addition, routine procedures performed solely for research purposes (e.g., additional diagnostic/follow-up tests) should be identified.

Procedures for treatment subjects

Table 1. Study procedures for treatment subjects.

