Visit Time point	Screening and baseline procedures	4-week visit (within 4 weeks of fracture)	8-week visit (8 +/- 1 weeks after fracture)	12-week visit (12 +/- 1 weeks after fracture)
Informed consent	X*			
Spine Fracture Clinic visit	X (if needed for routine care)	X	X	X
Physical Exam	X	X	X	X
Neck Disability Index		X	X	X
VAS Neck		X	X	X
(Eligibility confirmed by study team after screening labs completed and before study drug administration)				
Endocrinology Clinic visit (only if the patient is not recruited while inpatient)	X*			
Study drug teaching and first dose of Tymlos	X*			
Tymlos self-administration	X* (daily for 8 weeks after drug teaching)			
CMP	X*			
PTH	X*			
Phos	X*			
HbA1c	X*			
AP/Lateral XR	X	X	X	(X if required for routine care)
Flex/Ext XR				X
CT Cervical	X			X*
DEXA	X** (by time of 12-week visit)			
Phone check-in	X* (each week +/- 2 d after first dose for the 8-week treatment period)			

* These procedures are research-driven and deviate from routine care of treatment patients in clinic.

** The DEXA scan is completed for research purposes only if not previously completed within 12 months before consent for routine care purposes.

Spine fracture clinic (and endocrinology visit, for patients not recruited in the inpatient setting) involve medical history under routine care.

Neck Disability Index and VAS Neck physical function are questionnaires given to patients during the clinic visit and prior to medical evaluation. These take less than 10 minutes to fill out, they are validated, and they are standard/routine in many clinic visits. These questionnaires will provide secondary outcome measures.

The study drug (abaloparatide) is an FDA approved medication used to treat osteoporosis. It is a daily subcutaneous injection administered by the patient. This requires patient education.

CMP, PTH, Phos, and HbA1c are laboratory tests performed by venipuncture. Blood work includes complete metabolic profile, phosphorous, parathyroid hormone, and hemoglobin A1c. Many of these patients have osteoporosis at baseline and these tests allow us to screen, quantify, and subsequently manage their osteoporosis. This blood work is standard of care for evaluation and treatment of osteoporosis. In this study, CMP, PTH and Phos will be obtained as screening labs (see Screening Procedures, below). HbA1c

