levels are meant for baseline data collection as they relate to the ability to heal fractures, and are tested with screening labs to prevent need for additional blood draws for research purposes.

AP/Lateral XR and Flex/Ext XR is a standard set of X-rays of the cervical spine used to evaluate the secondary outcome of translational motion at the fracture.

CT Cervical spine is for research purposes at the 12-week mark only. This will be used to measure fracture union rate (the primary outcome).

The DEXA scan is a low dose x-ray scan used as a screening tool recommended for all women over the age of 65. The radiation is so low (significantly lower than a chest x-ray) that this machine and radiation is not formally regulated in the United States. Many of these patients have osteoporosis at baseline and this test allows us to screen, quantify, and subsequently manage their osteoporosis. *In this study*, DEXA scans will be obtained to evaluate bone health as it relates to the ability to heal a fracture. If a patient's T-score is ≤ -2.5 at the spine or hip in a DEXA scan obtained for research purposes, the study team will notify the patient of the finding and refer her/him for follow-up care, as appropriate.

Procedures for control cohort A (active control participants)

Table 2. Research procedures for control patients who provide written consent to active study participation (control cohort A).

Item	UVMMC	Via Mail
Informed consent	X	
Neck Disability Index	X	
VAS Neck	X	
Cervical CT Scan	X	
Flexion-extension cervical x-ray	X**	
Compensation		X*

* After completion of CT scan

** The XR is only obtained for research purposes if a flexion-extension cervical x-ray was not obtained 11 or more weeks after initiation of hard collar treatment as part of their routine care.

Procedures for control cohort B (review-only control participants)

Control cohort B includes subjects who

- (a) Previously had a cervical CT scan obtained after completion of their hard collar treatment under routine care; or
- (b) do not provide written consent to active study participation but provide verbal consent to allow the study team to collect existing information that is available from their treatment in the electronic medical record; or
- (b) are deceased and are not available for informed consent

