i. Once a prospective subject is identified, who initiates the informed consent discussion and answers questions presented by the subject or the subject's family?

Designated key personnel of the study will be able to initiate the informed consent discussion and answer questions presented by the subject or the subject's family.

ii. Where (in what setting) is the informed consent process initiated? How much time is the subject given to decide?

For the treatment subjects, ideally the informed consent process will be initiated in the hospital setting within a

day or two after the diagnosis. If the patient is diagnosed at an outside facility and presents to the outpatient spine clinic for follow up, the informed consent process would be initiated there.

For potential control subjects who are living at time of identification and have not previously had a cervical CT under routine care after completion of hard collar treatment; the informed consent process will be initiated either in person or via letter or email from [name]. Designated research personnel will follow-up in person or by phone within two weeks to inquire about interest in study participation. The same, approved recruitment phone script will be used whether it is in person or by phone.

- For participants interested in active study participation (*control cohort A*), written informed consent will be obtained in person at UVMMC in a private room, prior to study imaging or administration of the study questionnaires.
- For eligible control subjects who indicate at time of recruitment phone call that they are not interested in active study participation, the patient will be invited to verbally consent to participation in *control cohort B*. A verbal consent script has been developed for this purpose.

Potential control subjects who are living at time of identification and have previously had a cervical CT under routine care after completion of hard collar treatment will be approached using the approved verbal consent script described above. The verbal consent script offers the opportunity for (passive) participation in *control cohort B* and introduces the researcher as a member of [name] research team.

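### For living controls, an existing CT is tested against collar completion rather than the 11-13 week window of the primary outcome, and no rule says which CT is analysed when two exist

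*Combined protocol and SAP*

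**What the plan says.** Statistical Considerations defines the endpoint: "Primary outcome will be % bridging bone on CT scan at 12 weeks". For treated patients, Study Design and Table 1 put the research CT at 12 +/-1 weeks, which Table 1 counts from fracture. Neither makes collar removal a condition.

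For living controls, three places use collar completion as the test of an existing CT:

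- Study Design, Control subjects, describes the review-only group as including those who "previously had a cervical CT after completion of hard collar treatment under routine care".
- Procedures for control cohort B, first criterion: "Previously had a cervical CT scan obtained after completion of their hard collar treatment under routine care".
- Consent Process, item ii: living controls who "have previously had a cervical CT under routine care after completion of hard collar treatment will be approached using the approved verbal consent script", while those who "have not previously had a cervical CT under routine care after completion of hard collar treatment" are approached first for cohort A.

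For cohort A, Study Design states: "Consented active control subjects will then complete a CT scan of the cervical spine for comparison to those from our study group". It gives no time window for that scan, and Inclusion/Exclusion Criteria allow the fracture to be up to 10 years old at consent. The plain-film rule in the same section uses another anchor. A new film is taken "If flexion-extension cervical XR were not obtained 11 or more weeks after initiation of hard collar treatment as part of their routine care".

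**The concern.** The endpoint is tied to time since fracture, but the test of a control's existing CT is tied to the end of the collar. Because control collars last 12 +/-1 weeks, the end of the collar often falls inside the 11-13 week window or after it. A scan taken at the right time can therefore fail the test only because the collar was still on.

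A scan in the window is the best-timed primary value a control can supply, since it needs no correction for time since injury. If a later scan is analysed instead, the control fracture has had longer to heal than the treated fractures it is compared with. That would tend to raise bridging in controls and make a drug effect harder to see. The patient would also have a research CT, put at about 2.8 mSv in Risks/Benefits, that the endpoint did not need. With 12 controls planned, each is 1/12 = 8.3% of the group.

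**Working it through.** The plan states no figure on this point, so there is none to reproduce. The check is interval arithmetic on the plan's own windows.

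**Inputs**

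- Treated CT window: 12 +/-1 weeks after fracture, so weeks 11 to 13, or days 77 to 91 (Table 1).
- Control collar duration d: 12 +/-1 weeks, so 11 to 13 weeks (Historical Comparison Subjects, inclusion criterion 4).
- Delay s from fracture to collar start: not given. Assumed s = 0, with s = 1 week as a sensitivity case.
- Look-back: 10 years before consent (inclusion criterion 3).

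**Step 1. Part of the window before collar removal.** Collar end e = s + d. Width before removal = max(0, min(13, e) - 11), out of 2 weeks.

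| s (weeks) | d = 11 | d = 12 | d = 13 |
|---|---|---|---|
| 0 | min(13, 11) - 11 = 0 | min(13, 12) - 11 = 1 | min(13, 13) - 11 = 2 |
| 1 | min(13, 12) - 11 = 1 | min(13, 13) - 11 = 2 | min(13, 14) - 11 = 2 |

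With a collar started at fracture, 0 to 2 of the 2 weeks precede removal, and 1 week at the nominal 12-week duration. Any delay in starting the collar widens the gap, up to the full 2 weeks.

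**Step 2. Same scan day, opposite handling.** Take a routine CT on day 82, inside days 77-91. If the collar came off on day 80, the scan follows completion and the control is approached for cohort B. If it came off on day 88, the scan precedes completion and the control is approached for cohort A. Time since fracture is identical. These are illustrative dates, not trial records.

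**Step 3. What the second control then supplies.** On consent, a new CT is taken and is the one named for comparison. It falls after collar completion, with no stated upper limit. A fracture may be up to 10 x 365.25 / 7 = about 522 weeks old at consent.

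**Step 4. Is there a rule for two scans?** None was found. Sources of Materials says both existing records and research procedures supply data, and it lists CT scans for cohort A without saying which is read. The same gap arises for a control with one CT in the window and a second routine CT after the collar.

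**Step 5. Who is subject to the test.** Study Design and the cohort B criteria admit decliners and deceased controls by separate routes, on whatever records exist. Neither route carries the post-completion condition.

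**The case against.** The strongest reply is that this is a recruitment rule, not an analysis rule. It decides which consent approach a control receives, and no sentence says an earlier scan is discarded. That stands in part: replacement is an inference. It is a reasonable one, because only the new CT is named for the comparison, but the documented defect is the missing selection rule.

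A second reply is that such scans may not exist. Table 1 and its notes describe the treated group's 12-week CT as research-driven, and routine follow-up is by plain film. This stands. The cohort B criterion presupposes some routine CTs after the collar, but nothing shows any taken at weeks 11-13 with the collar on.

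Third, a scan after the end of treatment is a defensible anchor. The plain-film rule concerns a secondary outcome and is itself open-ended, so the two rules do not contradict each other. The contrast shows only that a time-based test was available.

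Two stronger readings are tempting and are not supported:

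- A reader might infer that no in-collar scan counts for any control, including decliners and the deceased. The separate cohort B routes rule this out.
- A reader might attach a size. If CT day and collar duration are each uniform over 15 days and independent, with the collar started at fracture, 105 of 225 day pairs (47%) put the CT before completion. That is a share of an unknown number of scans, and independence is doubtful because both events are scheduled around week 12. Converting it to a shift in union rate would need the number of affected controls and a later healing rate, neither of which the documents give. It would also describe a binary rate when the primary outcome is a continuous percentage.

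**Conclusion.** The point holds as a gap in the routing test and in scan selection. For living controls the stated test can set a well-timed scan aside in favour of a later, unwindowed one, and the plan does not say which would be analysed. The likely direction is towards controls, on the assumption that bridging does not decline with further time. The size cannot be given, and the number affected may be zero.

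This is a cheap improvement, not a major flaw. The larger timing problem is that cohort A scans, and routine scans accepted as post-completion, have no upper time limit. Correcting this test alone leaves that in place.

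**What to change.** In Study Design (Control subjects), Procedures for control cohort B, and Consent Process item ii:

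- Keep the post-completion test, and accept in addition any routine cervical CT obtained 11-13 weeks after fracture, whether the collar was on or off, provided it can be read by the protocol's method (1 mm coronal and sagittal sections, orthogonal reconstruction).
- State that such a CT is that control's primary-outcome scan and takes precedence over any later routine or research CT.
- Leave the routing of all other controls as it is.
- Report time from fracture to CT by group.
- Reconcile Sources of Materials, which lists CT scans for cohort A but only radiographs for cohort B.

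Settle the rule before any control scan is read. The cost is a wording change in these places and the consent scripts, plus a date and readability check at chart review. No procedure is added, and some research CTs may be avoided. The downside is that some routine scans may have lower resolution than research scans, which is why the readability condition is needed.
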